APPENDIX A: CLINICAL RISK/ BENEFIT ANALYSIS

Edwards Lifesciences

Protocol Number: 2017-05

Clinical Risk/ Benefit Analysis

1.0 SUMMARY

The objective of this clinical trial is to evaluate the safety and efficacy of the Edwards Cardioband System for transcatheter mitral annular reduction in treating patients with functional mitral regurgitation.

Risks to patients undergoing the Edwards Cardioband System procedure are listed below. The risks of participation are offset by the significant potential for clinical and functional benefits to patients with functional mitral regurgitation that comes through improving mitral valve function.

2.0 POTENTIAL BENEFITS

The potential benefit to study patients outweighs the risks of participation in this study. The benefits may include but are not limited to, the following:

- Clinical improvement (e.g. NYHA Class, 6 minute walk test)
- Functional improvement (e.g. mitral valve function)
- Overall advancement of medical and scientific knowledge which may benefit future patients with similar conditions may be gained through this clinical study.

There may also be other benefits that are unforeseen at this time.

3.0 POTENTIAL RISKS

Adverse events that are anticipated in this clinical study are believed to be consistent with those associated with other minimally invasive surgical and catheter-based procedures. Complications may occur at any time during the procedure, post-procedure or follow-up period.

Anticipated or potential adverse events that may occur during the study are listed in Table 7. These events may be associated with the Edwards Cardioband System, transcatheter procedure, stress-induced tests (e.g. TEE, TTE, MSCT scan, exercise tolerance, etc.), ancillary procedures or may occur in the heart failure population over time. Possible outcomes of the adverse events include reoperation, explant of the Edwards Cardioband, permanent disability or death. There may also be other risks that are unforeseen at this time.

Table 7: Anticipated or Potential Adverse Events

Abnormal laboratory values (e.g. electrolyte imbalance)
Allergic reaction/hypersensitivity to contrast media, medication, or
device materials
Anaphylactic shock
Anemia including hemolytic anemia
Anesthesia reactions
Angina pectoris
Arrhythmias and conduction system disorders (e.g. ventricular or
atrial tachycardia or fibrillation; AV block) which may require
permanent pacemaker implantation
Atrial septal defect requiring intervention
Bleeding
Cardiac arrest
Cardiac Tamponade
Cardiogenic shock
Cardiovascular injury (e.g. damage of ventricle, ventricular septal
perforation, myocardium or valvular structures including annulus
rupture)
Cerebrovascular event (e.g. TIA, Stroke, neurologic changes)
Circumflex Artery Occlusion
Circumflex Artery Perforation
Conversion to an open cardiac surgery, including extracorporeal
circulation
Coronary Artery Occlusion
Coronary Artery Perforation
Death
Deep venous thrombus (DVT)
Device associated endocarditis
Device dehiscence

PROTOCOL NUMBER: 2017-05

Device embolization, migration, malposition, or deployment in
unintended location
Device explantation
Device malfunction/ mechanical failure of device, delivery system and/or accessories
Device thrombosis
Dyskinesia, paralysis, permanent disability (new onset or worsening)
Dyspnea
Edema
Emboli/ Embolization (e.g. air, calcific material, thrombus)
Esophageal irritation or injury (e.g. perforation)
Exercise intolerance or weakness
Failure of the valvular apparatus due to progression of disease
Failure to deliver the device to the intended site
Fever
Groin hematoma
Heart failure or low cardiac output
Heart murmur
Hematoma
Hemodynamic compromise
Hemolysis
Hemorrhage
Hospitalization for heart failure
Hypertension
Hypotension
Implantation of second transcatheter mitral repair device
Implantation of surgical annuloplasty device
Inadequate repair of the valvular structure
Infection including endocarditis and septicemia
Inflammation
Mitral stenosis
Mitral valve injury, or worsening of mitral regurgitation
Multi-system organ failure
Myocardial infarction
Nausea/vomiting
Nerve injury
Non-structural device dysfunction (e.g., regurgitation)
Pain

PROTOCOL NUMBER: 2017-05

[figure not shown]
Perforation or damage of vessels or tissue, myocardium or valvular
structures
Pericardial effusion, may require drainage
Peripheral edema
Peripheral ischemia
Pleural effusion
Pneumonia
Prolonged ventilation
Pulmonary edema
Pulmonary embolism
Renal insufficiency or failure
Re-operation or emergency cardiac surgery
Respiratory compromise or respiratory failure
Retroperitoneal bleeding
Right heart failure
Stroke
Structural deterioration or degeneration of device (e. g. tear, suture line disruption, breakage, wear, calcification, anchor detachment)
Syncope or dizziness
Thrombus formation
Transvalvular flow disturbance
Vascular access (e.g. femoral entry site) complications (e.g.
bleeding, hematoma, arteriovenous fistula, arterial occlusion,
pseudoaneurysm, wound healing disorder, pain)
Vascular damage (e.g. perforation, dissection, contrast media
extravasation, spasm)
Vessel spasm
Worsening heart failure symptoms

4.0 MINIMIZATION OF RISKS

Measures which will be taken to minimize risks related to the study include:

• Investigators in this study will be selected based on their experience in treating patients with mitral regurgitation and performing structural heart interventional procedures.

PROTOCOL NUMBER: 2017-05

- Investigators will be trained in proper procedure performance and device operation prior to patient treatments. Training will include didactic and handson training with the Edwards Cardioband System.
- Well-defined clinical study protocol, including specific inclusion/ exclusion criteria to enroll appropriate patients in the trial.
- A Central Screening Committee (CSC) ensures final eligibility of patients for participation in the study.
- Close patient monitoring during the implant procedure and follow-up period.
- Ongoing monitoring of study data and results, including the use of independent Clinical Events Committee (CEC) and Data Safety Monitoring Board (DSMB).

5.0 CONCLUSION

This clinical study is justified because the study Sponsor and clinical Investigators believe the potential benefits outweigh the potential risks.

APPENDIX B: STUDY DEFINITIONS

Endpoints identified in the Clinical Events Committee (CEC) Charter will be adjudicated by the independent Clinical Events Committee. A detailed CEC Charter will further define the endpoint definitions. In case of inconsistency between the protocol and the CEC Charter, the CEC Charter will be the final determining document.

ACCESS SITE

Any location (arterial or venous) traversed by a guide-wire, a catheter or a sheath.

ACCESS SITE AND VASCULAR COMPLICATIONS REQUIRING INTERVENTION

Complications (i.e. dissection, perforation, arteriovenous fistula, pseudoaneurysm, retroperitoneal hemorrhage, thromboembolism etc.) requiring intervention (percutaneous or surgical).

ATRIAL FIBRILLATION (AF) – Heart Rhythm Society Guidelines

Paroxysmal: Recurrent (≥ 2) atrial fibrillation episodes that terminate spontaneously within 7 days.

Persistent: Atrial fibrillation that is sustained beyond 7 days, or lasting less than 7 days but necessitating pharmacologic or electrical cardioversion.

Longstanding Persistent AF: Continuous atrial fibrillation of greater than 1 year duration.

Permanent: Atrial fibrillation in which cardioversion has failed or not been attempted.

BLEEDING (MVARC)

Minor

Any overt, actionable sign of hemorrhage (e.g., more bleeding than would be expected for a clinical circumstance, including bleeding found by imaging alone) that meets ≥ 1 of the following: requiring nonsurgical medical intervention by a health care professional; leading to hospitalization or increased level of care; prompting evaluation; or requires 1 or 2 units of whole blood or packed red blood cell (RBC) transfusion and otherwise does not meet criteria for major, extensive, or life threatening.

Major bleeding

PROTOCOL NUMBER: 2017-05

Overt bleeding either associated with a drop in the hemoglobin level of \geq 3.0 g/dl or requiring transfusion of ≥3 units of whole blood or packed RBC AND does not meet the criteria of life-threatening or extensive bleeding.

Extensive

Overt source of bleeding with drop in hemoglobin of ≥ 4 g/dl or whole blood or packed RBC transfusion

Life-threatening

Bleeding in a critical organ, such as intracranial, intraspinal, intraocular, or pericardial necessitating surgery or intervention, or intramuscular with compartment syndrome OR bleeding causing hypovolemic shock or hypotension (systolic blood pressure < 90 mm Hg lasting > 30 min and not responding to volume resuscitation) or requiring significant doses of vasopressors or surgery.

Fatal bleeding

Bleeding adjudicated as being a proximate cause of death. Severe bleeding adjudicated as being a major contributing cause of a subsequent fatal complication, such as MI or cardiac arrest, is also considered fatal bleeding.

CARDIOVASCULAR DEATH (MVARC)

Cardiovascular death is defined as any of the following contributing conditions:

- Heart failure (sub-classified into left ventricular vs. right ventricular dysfunction)
- Myocardial infarction
- Major bleeding
- Thromboembolism
- Stroke
- Arrhythmia and conduction system disturbance
- Cardiovascular infection and sepsis (e.g., mediastinitis and endocarditis)
- Tamponade
- Sudden, unexpected death
- Other cardiovascular
- Device failure

PROTOCOL NUMBER: 2017-05

• Death of unknown cause (adjudicated as cardiovascular)

Non cardiovascular Death (MVARC)

Any death in which the primary cause of death is clearly related to another condition:

- Non cardiovascular infection and sepsis (e.g., pneumonia)
- Renal failure
- Liver failure
- Cancer
- Trauma
- Homicide
- Suicide
- Other noncardiovascular

FUNCTIONAL MITRAL REGURGITATION

Mitral regurgitation (≥3+ must be present for inclusion) accompanied by global or regional left ventricular wall motion abnormalities AND dilatation of the mitral annulus, with no significant abnormalities of the mitral apparatus, except mild focal thickening thought to be related to aging. No leaflet flail or other evidence of degenerative MR may be present, even in the presence of global or regional LV systolic dysfunction.

HEART TEAM

The local "Heart Team" (in accordance with MVARC) will consist of a multidisciplinary team which will assess the appropriateness of the patient for the protocol and as a minimum will consist of a heart failure/valve cardiologist, an interventional cardiologist skilled in the relevant access and device implantation procedures, a mitral valve cardiac surgeon and an imaging specialist.

HOSPITALIZATION (ALL-CAUSE)

Defined as admission to inpatient unit or ward in the hospital for ≥ 24 hours, including emergency department stay. Hospitalizations planned for pre-existing conditions are excluded unless there is worsening of baseline condition.

HEART FAILURE HOSPITALIZATION

Both of the following additional criteria are present:

- Symptoms, signs and/or laboratory evidence of worsening heart failure
- Administration of intravenous or mechanical heart failure therapies

Patients hospitalized with heart failure are further sub-classified as:

- Primary heart failure hospitalization, including heart failure secondary to other cardiac related hospitalization such as for myocardial infarction.
- Secondary heart failure hospitalization heart failure has occurred during an otherwise non-cardiac related hospitalization.

OTHER CARDIOVASCULAR HOSPITALIZATION

Including hospitalizations such as for coronary artery disease, acute myocardial infarction, hypertension, cardiac arrhythmias, cardiomegaly, pericardial effusion, atherosclerosis, stroke, or peripheral vascular disease without qualifying heart failure.

NON-CARDIOVASCULAR HOSPITALIZATION

Hospitalizations that are not due to heart failure or other cardiovascular hospitalizations, as defined above.

LEFT CIRCUMFLEX ARTERY INJURY REQUIRING INTERVENTION

Injury to the left circumflex (LCX) artery which requires intervention may include occlusion, perforation, laceration, dissection, ligation, suture or anchor misplacement. Other potential causes may include a thrombus or hematoma formation due to surgical trauma. Vasospasm of the LCX artery is excluded in this definition unless it requires percutaneous intervention.

PROTOCOL NUMBER: 2017-05

MITRAL VALVE STENOSIS

Defined as a mitral valve orifice area of less than 1.5 cm² as measured by the

Echocardiography Core Laboratory.

MYOCARDIAL INFARCTION

Myocardial infarction (MI) classification and criteria for diagnosis is defined as follows:³¹

1. Peri-procedural MI (≤ 48 hours after Edwards Cardioband System procedure)

1.1. In patients with normal baseline CK-MB (or cTn):

Peak Creatinine Kinase myocardial b fraction (CK-MB) measured within 48

hours of Edwards Cardioband System implantation rises to ≥10x of the local

laboratory upper limit of normal (ULN) plus new ST-segment elevation or

depression of ≥1 mm in ≥ 2 contiguous leads (measured 80 ms after the J-

point) or to ≥5x ULN with new pathological Q waves in ≥2 contiguous leads or

new persistent LBBB.

1.2. In patients with elevated baseline CK-CB (or cTn):

The CK-MB (or cTn) rises by an absolute increment equal to those levels

recommended above from the most recent pre-procedure level plus new ECG

changes as described above.

1.3. In patients without CK-MB measurements and a normal baseline cTn,

A Cardiac Troponin (cTn (I or T)) level measured within 48 h of the PCI rises to

≥70x the local laboratory ULN *plus* new ST-segment elevation or depression

of \geq 1 mm in \geq 2 contiguous leads (measured 80 ms after the J-point) OR \geq 35x

ULN with new pathological Q waves in ≥ 2 contiguous leads or new persistent

LBBB.

2. Spontaneous MI (> 48 hours after Edwards Cardioband System procedure)

Page **102** of **113**

PROTOCOL NUMBER: 2017-05

Detection of rise and/or fall of cardiac biomarkers (preferably cTn) with at least one value

above the 99th percentile of the upper reference limit (URL) or ULN in the absence of

URL, together with at least one of the following:

2.1. Symptoms of ischemia

2.2. ECG changes indicative of new ischemia (new ST - segment or T- wave

changes or new LBBB) or new pathological Q waves in 2 contiguous leads

2.3. Imaging evidence of new loss of viable myocardium or new regional wall

motion abnormality

3. MI associated with sudden, unexpected cardiac death

Sudden cardiac death or cardiac arrest, often with symptoms suggestive of myocardial

ischemia, and accompanied by presumably new ST-segment elevation or new LBBB

and/or evidence of fresh thrombus by coronary angiography and/or at autopsy, but death

occurs before blood samples could be obtained or at a time before the appearance of

cardiac biomarkers in the blood.

4. Pathological findings of an acute myocardial infarction

MODIFIED RANKIN SCALE SCORE DESCRIPTIONS

0: No symptoms at all

1: No significant disability despite symptoms; able to carry out all usual duties and

activities

2: Slight disability; unable to carry out all previous activities, but able to look after own

affairs without assistance

3: Moderate disability; requiring some help, but able to walk without assistance

4: Moderately severe disability; unable to walk without assistance and unable to attend

to own bodily needs without assistance

5: Severe disability; bedridden, incontinent and requiring constant nursing care and

attention

Page **103** of **113**

PROTOCOL NUMBER: 2017-05

6: Dead

NEW YORK HEART ASSOCIATION CLASSIFICATION (NYHA CLASS)

Class I Patients with cardiac disease but

without resulting limitations of physical

activity.

Class II Patients with cardiac disease resulting

in slight limitation of physical activity.
Patients are comfortable at rest.
Ordinary physical activity results in fatigue, palpitation, dyspnea, or anginal

pain.

Class III Patients with cardiac disease resulting

in marked limitation of physical activity. Patients are comfortable at rest. Less than ordinary physical activity causes fatigue, palpitation

dyspnea, or anginal pain.

Class IV Patients with cardiac disease resulting

in inability to carry on any physical activity without discomfort. Symptoms

of cardiac insufficiency or of the

anginal syndrome may be present even

at rest. If any physical activity is undertaken, discomfort is increased.

PERICARDIAL EFFUSION REQUIRING DRAINAGE

Major pericardial effusion requiring drainage, also known as cardiac tamponade (CT) is a life-threatening, slow or rapid compression of the heart due to the pericardial accumulation of fluid, pus, blood, clots or gas as a result of inflammation, trauma, rupture of the heart, aortic dissection or iatrogenic causes (invasive procedure-related). Cardiac tamponade meets the MVARC definition for device-related technical failure issues and complications and the MVARC definition for life threatening bleeding in a critical organ.

PROTOCOL NUMBER: 2017-05

REINTERVENTION

Any intervention on the previously implanted study device (repair, alteration or replacement)

STROKE and TIA

Acute episode of a focal or global neurological deficit with at least one of the following: change in level of consciousness, hemiplegia, hemiparesis, numbness or sensory loss affecting one side of the body, dysphasia or aphasia, hemianopia, amaurosis fugax, or other neurological signs or symptoms consistent with stroke.

Cases will be categorized as either

- 1) Stroke Duration of a focal or global neurological deficit ≥24 hours; OR <24 hours, if available neuroimaging documents a new hemorrhage or infarct; OR the neurological deficit results in death
- 2) TIA Duration of a focal or global neurological deficit <24 hours, any variable neuroimaging does not demonstrate a new hemorrhage or infarct

Stroke classification

Ischemic – An acute episode of focal cerebral, spinal, or retinal dysfunction caused by infarction of central nervous system tissue

Hemorrhagic – An acute episode of focal or global cerebral or spinal dysfunction caused by intraparenchymal, intraventricular, or subarachnoid hemorrhage

A stroke may be classified as undetermined if there is insufficient information to allow categorization as ischemic or hemorrhagic

Stroke definitions

Disabling stroke – a mRS score of 2 or more at 90 days and an increase of at least one mRS category from an individual's pre-stroke baseline

Non-disabling stroke – a mRS score of less than 2 at 90 days or one that does not result in an increase of at least one mRS category from an individual's pre-stroke baseline

Patients with non-focal global encephalopathy will not be reported as a stroke without unequivocal evidence of cerebral infarction based upon neuroimaging studies (CT scan or Brain MRI).

RENAL COMPLICATIONS (Long-Term)

Long-term Renal Complication is defined as onset of renal replacement therapy

ACCESS SITE AND VASCULAR COMPLICATIONS (MVARC)

I. Vascular complications

- A. Major access site vascular complications, including:
 - i. Aortic dissection or aortic rupture, or
 - ii. Access site-related[†] arterial or venous injury (dissection, stenosis, ischemia, arterial, or venous thrombosis including pulmonary emboli, perforation, rupture, arteriovenous fistula, pseudoaneurysm, hematoma, retroperitoneal hematoma, atrial septal defect‡), irreversible nerve injury, or compartment syndrome resulting in death; hemodynamic compromise; life-threatening, extensive, or major bleeding (MVARC bleeding scale); visceral ischemia; or neurological impairment, or
 - iii. Distal embolization (noncerebral) from a vascular source requiring surgery or resulting in amputation or irreversible end-organ damage,
 - iv. Unplanned endovascular or surgical interventions resulting in death; life-threatening, extensive, or major bleeding (MVARC bleeding scale); visceral ischemia; or neurological impairment
- B. Minor access site vascular complications, including:
 - i. Access site arterial or venous injury (dissection, stenosis, arterial, or venous thrombosis including pulmonary emboli, ischemia, perforation, rupture, arteriovenous fistula, pseudoaneurysm, hematoma, retroperitoneal hematoma, atrial septal defect‡) not resulting in death; life-threatening, extensive, or major bleeding (MVARC scale); visceral ischemia; or neurological impairment, or
 - ii. Distal embolization treated with embolectomy and/or thrombectomy not resulting in amputation or irreversible end-organ damage, or
 - iii. Any unplanned endovascular stenting or unplanned surgical intervention not meeting the criteria for a major vascular complication, or

iv. Vascular repair (via surgery, ultrasound-guided compression, transcatheter embolization, or stent-graft)

II. Cardiac structural complications due to access-related issues

- A. Major cardiac structural complications, including:
 - i. Cardiac perforation* or pseudoaneurysm resulting in death, lifethreatening bleeding, hemodynamic compromise, or tamponade, or requiring unplanned surgical or percutaneous intervention
- B. Minor cardiac structural complications, including:
 - i. Cardiac perforation* or pseudoaneurysm not meeting major criteria

*Including the left ventricle, left atrium, coronary sinus, right atrium, and right ventricle

†May arise from the access procedure per se or complications from vascular closure devices

‡Meeting pre-specified criteria for a hemodynamically significant shunt, or requiring unplanned percutaneous or surgical closure

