5.2 Primary Safety Endpoint (Evaluated through 30 Days post procedure) [Device Group only]

Overall rate of device and procedure related Major Adverse Events (MAEs) through 30 days post-procedure (including death, stroke, myocardial infarction, pericardial effusion requiring drainage, left circumflex coronary artery injury requiring intervention, mitral valve reintervention and access site and vascular complications requiring intervention. The primary safety endpoint was chosen to detect any concerns relating to safety of the Edwards Cardioband System implantation procedure.

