### 3.4 **Primary Safety Endpoints – Device Group Only (30 Days)**

Overall rate of device and procedure related major adverse events (MAEs), which includes:

- a. Death
- b. Stroke
- c. Myocardial infarction
- d. Pericardial effusion requiring drainage
- e. Left circumflex coronary artery injury requiring intervention
- f. Mitral valve reintervention
- g. Access site and vascular complications requiring intervention

The primary safety endpoints were chosen to detect any concerns relating to safety of the Edwards Cardioband System implantation procedure.

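### Appendix B defines the drained-effusion safety component as tamponade, so an effusion drained without cardiac compression fails that component and may be missed in the 30-day MAE rate

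*Protocol*

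**What the plan says.** The component is named by treatment alone. Protocol 5.2 places it among the MAEs as "myocardial infarction, pericardial effusion requiring drainage, left circumflex coronary artery injury requiring intervention". SAP 3.4 lists it as "Pericardial effusion requiring drainage" and gives no definition. It is also a secondary safety endpoint in its own right (Protocol 5.3, item 4; SAP 3.5, item d).

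The only definition in the two documents is in Protocol Appendix B, under the heading for this event: "Major pericardial effusion requiring drainage, also known as cardiac tamponade (CT) is a life-threatening, slow or rapid compression of the heart". This adds a grade (major), equates the event with tamponade and describes a life-threatening state.

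The preamble to Appendix B gives precedence to a document outside the protocol and SAP: "In case of inconsistency between the protocol and the CEC Charter, the CEC Charter will be the final determining document".

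The safety analysis is descriptive. Protocol 13.4.3 and SAP 8.3 call for rates with 95% confidence intervals and state no hypothesis test or performance goal.

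**The concern.** The endpoint name and its definition select different patients. The name takes in every effusion that had to be drained. The definition takes in only those that compressed the heart. A patient drained before compression developed would meet the first and not the second.

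This matters because the implant is anchored along the posterior mitral annulus (Protocol 1.2; SAP 7.5 tabulates the number of anchors). Protocol 5.2 says that the primary safety endpoint was chosen to detect safety concerns with the implantation procedure. A component narrower than its label would understate the effusion rate shown to readers who see only the label, and it could lower the composite as well. Two adjudicators, one working from the name and one from the definition, could classify the same patient differently.

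**Working it through.** No figure in the plan can be reproduced here. The documents give no expected MAE rate, effusion rate or safety sample size. The check is therefore a comparison of definitions, followed by the effect per patient.

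**1. Is the tamponade condition in line with the rest of Appendix B?**

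- Left circumflex injury requiring intervention turns on whether the injury needed intervention.
- Access site and vascular complications requiring intervention turn on percutaneous or surgical intervention, after an open-ended list that includes perforation.
- The MVARC bleeding scale classes pericardial bleeding as life-threatening when surgery or intervention is needed, without requiring compression.
- Major cardiac structural complications list tamponade and intervention as alternatives: "hemodynamic compromise, or tamponade, or requiring unplanned surgical or percutaneous intervention".

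The other two MAE components whose names carry a treatment qualifier are thus defined by treatment. The effusion component alone adds a physiological condition that its name lacks. A drained pericardial bleed without compression could be life-threatening on the bleeding scale and still fail the effusion component. Bleeding is not itself an MAE component.

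**2. What happens to a drained effusion under the written text?**

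| Drained effusion | Effusion component | MAE composite |
|---|---|---|
| With cardiac compression | Counts | Counts |
| No compression, from an access-related cardiac perforation | Fails | Can count as an access site and vascular complication requiring intervention |
| No compression, anchor-related or inflammatory | Fails | Not clearly captured |
| No compression, patient has another MAE | Fails | Counts through the other MAE |

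The second row rests on the short definition of access site and vascular complications and on Part II of the MVARC text under the same heading, which covers perforation of the cardiac chambers. The third row differs because Part II is limited to access-related problems, and Appendix B defines an access site as an arterial or venous location crossed by a wire, catheter or sheath. The composite also counts only device- and procedure-related events, so an inflammatory effusion would have to be judged related to matter there.

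In the second row the composite may be intact, but the event moves from secondary safety endpoint 4 to endpoint 6. The individual effusion rate is low in every row except the first.

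**3. Effect per patient**

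- Device patients: 375 × 2/3 = 250 (planned size and allocation, Protocol Section 4, Study Design).
- One missed patient with no other MAE: 1/250 = 0.4 percentage points.

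Illustration with assumed counts and exact (Clopper-Pearson) 95% intervals:

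| MAEs recorded (assumed) | Missed (assumed) | Recorded rate | Rate with missed patients added |
|---|---|---|---|
| 15 | 1 | 6.0% (3.4 to 9.7) | 16/250 = 6.4% (3.7 to 10.2) |
| 15 | 5 | 6.0% (3.4 to 9.7) | 20/250 = 8.0% (5.0 to 12.1) |
| 25 | 5 | 10.0% (6.6 to 14.4) | 30/250 = 12.0% (8.2 to 16.7) |

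**The case against.** **The Charter controls.** Appendix B says that the Charter will define endpoints further and prevails in a conflict. This stands as a limit: from these documents nobody can say that any event will be lost. It does not remove the inconsistency. A broader Charter would leave the protocol definition wrong, and a Charter that copies Appendix B would leave the gap in place.

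**The definition sets no hemodynamic threshold.** It speaks of slow or rapid compression under a heading that names drainage. An adjudicator could accept that a growing effusion judged to need drainage meets it. This stands in part: some such patients would be counted. The outcome would then rest on individual judgement, while the text still calls the event tamponade and life-threatening.

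**Stronger readings that a reader might infer.**

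- *That drained effusions without tamponade do not count in the MAE rate, or that major cardiac structural complications are outside it.* The documents do not support either. Structural complications sit under the access site and vascular heading, and an access-related perforation that is drained can enter the composite that way.
- *That Clinical Success is generally inflated.* Clinical Success requires Procedural Success, which already fails with a surgical or percutaneous intervention before discharge (Protocol 5.5, SAP 3.7). Drainage in hospital is naturally read as such an intervention. At most, drainage after discharge is affected.
- *That the risk table proves two separate endpoints.* Table 7 lists "Cardiac Tamponade" apart from "Pericardial effusion, may require drainage", but its entries overlap freely (bleeding and hemorrhage, for example), and its effusion entry also covers undrained cases. It is weak support, and the point does not rest on it.

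**Limited consequence.** Safety is a Device-only rate with a confidence interval, and the analysis sections show no pass or fail decision. Drained effusions would still be reported and tabulated as adverse events (Protocol 11.5, SAP 9.2). This stands and limits the weight of the point.

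**Conclusion.** The inconsistency is real. As written, Appendix B excludes an effusion drained without cardiac compression from a component whose name includes it, so the individual effusion rate is understated. The MAE composite is understated only for patients whom no other component captures, mainly those with effusions not due to an access-related perforation, and only if the CEC Charter does not define the event more broadly.

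The firm figure is 0.4 percentage points per missed patient at 250 Device patients. The total cannot be derived. If 2% to 4% of Device patients were drained and a third to a half of those had no tamponade, 250 × 0.02 × 1/3 = 1.7 to 250 × 0.04 × 1/2 = 5 patients would be affected, or 0.7 to 2.0 points. Both inputs are assumptions without a source in the documents, and the product presumes that no other component captures the patient. It should not be read as an estimate: the effect on the composite could be zero.

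**What to change.** Before adjudication, align Appendix B and the CEC Charter with the endpoint name. Count any pericardial effusion that is drained through 30 days, with or without hemodynamic compromise, and report tamponade as a subset. Have the SAP point to that definition, since SAP 3.4 and 3.5 give none.

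The cost is one definition in the protocol and the Charter, plus a cross-reference in the SAP. No new data are needed. The downside is that the reported effusion and MAE rates may be slightly higher. If the Charter already uses the broader definition, only the Appendix B text and the SAP reference need to change.
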